5.3 Handling of Missing data	16
6. General Considerations for Data Analyses.....	16
6.1 Data Summaries	16
6.2 Graphical Displays	17
7. Study Variable List.....	21
8. Reference.....	38

1. Introduction

Kawasaki disease (KD), an acute systematic vasculitis, has been reported worldwide nowadays and more prevalent in Asia. Coronary artery lesion (CAL) is the most important complication and one of the main predictors to the long-term prognosis of KD. CAL can induce coronary artery aneurysm (CAA), occlusion, myocardial ischemia, myocardial infarction and even death, making KD a major cause of the acquired heart diseases in children. The large dose of intravenous immunoglobulin, together with aspirin (abbreviated as IVIG treatment) administered during the acute phase of KD has been well proved in reducing the occurrence of CALs. Given certain proportion of patients response poorly to this treatment, which is commonly linked with higher risk of CAL, it is worth exploring whether more aggressive treatments are able to achieve better effectiveness in reducing the incidence of CAL or not. Corticosteroid, preferred in the treatments of majority of vasculitis, remains controversial in the acute phase treatment of KD. Several studies suggest that the therapy time, regimen and the targeted people require careful considerations in the corticosteroid's treatment in KD. It is still under arguing that using corticosteroids in the initial treatment benefits all the KD patients rather than those with higher risk of IVIG resistance.

The purpose of this Statistical Analysis Plan (SAP) is to define the outcome variables, statistical methods and analysis strategies for a multicenter open-label randomized controlled trial. The trial aims to evaluate the effects of two therapies in reducing the incidence of CAL for children with acute KD: conventional IVIG treatment plus prednisolone (the experimental arm) and only IVIG treatment (the control arm).

2. Study Objective and Outcomes

2.1 Study Objective

This is a superiority randomized controlled trial, aiming to provide high quality evidence for

supporting effects and safety of current treatment combining steroid (corticosteroids) in the IVIG treatment plan for newly onset Kawasaki disease pediatric patients. The primary objective is to evaluate the hypothesis that IVIG treatment plus prednisolone will reduce the incidence of CAL at 1 month of illness comparing with the conventional IVIG treatment. The secondary objectives include comparing the need of additional treatment or not and duration of fever after initial treatment, occurrence of CAL after 1 month of illness onset, changes in laboratory data between two treatment groups, and serious adverse events.

2.2 Outcomes

2.2.1 Primary Outcome

The primary outcome is the occurrence of coronary artery lesions (CAL) at one month from disease onset. Two-dimensional echocardiography will be performed to evaluate CAL at six time points (at admission before treatment as the baseline, 2th week (± 2 days), 1th month (± 5 days), 3th month (± 5 days), 6th month (± 5 days), and 12th month (± 5 days), respectively). The examination included the diameter of the left main coronary artery (LMCA), the left anterior descending artery (LAD), the left circumflex coronary artery (LCX), and the proximal and middle segments of the right coronary artery (RCA). Z scores of each coronary artery will be calculated¹, and the occurrence of CAL is defined as $z \geq 2$ of any coronary artery, including LMCA, LAD, LCX, and the proximal and middle segment of the RCA.

(Time Frame: at one month of illness) (Type: repeatedly measured binary variable)

2.2.2 Secondary Outcomes

- 1) Changes in z score of LMCA from admission. Data will be measured at six time points of illness: enrollment, 2th week (± 2 days), 1th month (± 5 days), 3th month (± 5 days), 6th month (± 5 days) and 12th month (± 5 days), respectively.

(Time Frame: from admission to 12 months of illness) (Type: repeatedly measured continuous

variable)

2) Changes in z score of LAD from enrollment. Data will be measured at six time points of illness: enrollment, 2th week (± 2 days), 1th month (± 5 days), 3th month (± 5 days), 6th month (± 5 days) and 12th month (± 5 days), respectively.
(Time Frame: from admission to 12 months of illness) (Type: repeatedly measured continuous variable)

3) Changes in z score of LCX from enrollment. Data will be measured at six time points of illness: enrollment, 2th week (± 2 days), 1th month (± 5 days), 3th month (± 5 days), 6th month (± 5 days) and 12th month (± 5 days), respectively.
(Time Frame: from admission to 12 months of illness) (Type: repeatedly measured continuous variable)

4) Changes in z score of the proximal segment of RCA from enrollment. Data will be measured at six time points of illness: enrollment, 2th week (± 2 days), 1th month (± 5 days), 3th month (± 5 days), 6th month (± 5 days) and 12th month (± 5 days), respectively.
(Time Frame: from admission to 12 months of illness) (Type: repeatedly measured continuous variable)

5) Changes in z score of the middle segment of RCA from enrollment. Data will be measured at six time points of illness: enrollment, 2th week (± 2 days), 1th month (± 5 days), 3th month (± 5 days), 6th month (± 5 days) and 12th month (± 5 days), respectively.
(Time Frame: from admission to 12 months of illness) (Type: repeatedly measured continuous variable)

6) Need for additional treatment or not. The acute KD patients in both arms resistant to the initial IVIG therapy will be given additional treatment, which will be determined by the prescription record.
(Time Frame: at one month of illness) (Type: binary variable)

7) Duration (hours) of fever (defined as an axillary temperature <37.5 for more than 24 hours) after initiation of initial IVIG among participates of two arms.
(Time Frame: from initiation of initial IVIG infusion to the first record of being afebrile) (Type: time-to-event variable)

8) Change in serum C-reactive protein (CRP) concentration from admission to 72 hours after

completion of initial IVIG infusion.

(Time Frame: from admission to 72 hours after completion of initial IVIG infusion) (Type: continuous variable)

- 9) Serious adverse events (including death, hypertension, severe infection, allergic reactions, heart failure, thrombosis, etc.) will be recorded.

(Time Frame: from admission to 3 months of illness) (Type: character variable)

2.2.3 Exploratory Outcomes

The following exploratory outcomes were added by authors during manuscript drafting or suggested by reviewers during revision.

- 1) Occurrence of medium-to-giant CAAs. CAL classification was based on the maximum z score according to the 2017 American Heart Association guideline². Medium CAA was defined as a maximum z score ≥ 5 to < 10 , and all internal diameters < 8 mm; large or giant CAA was defined as a maximum z score ≥ 10 , or any internal diameter ≥ 8 mm. Data were and will be collected at six time points of illness: enrollment, 2th week (± 2 days), 1th month (± 5 days), 3th month (± 5 days), 6th month (± 5 days) and 12th month (± 5 days), respectively.

(Time Frame: from admission to 12 months of illness) (Type: repeatedly measured binary variable)

- 2) Occurrence of large/giant CAAs. Data were and will be collected at six time points of illness: enrollment, 2th week (± 2 days), 1th month (± 5 days), 3th month (± 5 days), 6th month (± 5 days) and 12th month (± 5 days), respectively.

(Time Frame: from admission to 12 months of illness) (Type: binary variable)

- 3) Occurrence of CAL progression within 3 months of illness onset in all participants and those with CAL at baseline. CAL progression was defined as an increment in the z score ≥ 1 from baseline in any coronary artery (LMCA, LAD, LCX, proximal and middle segments of RCA) at any given time point within 3 months of illness onset.

(Time Frame: from admission to 3 months of illness) (Type: binary variable)

- 4) Changes in absolute diameters of LMCA, LAD, LCX, the proximal and middle segments of

RCA from enrollment. Data were and will be collected at six time points of illness: enrollment, 2th week (± 2 days), 1th month (± 5 days), 3th month (± 5 days), 6th month (± 5 days) and 12th month (± 5 days), respectively.

(Time Frame: from admission to 12 months of illness) (Type: repeatedly measured continuous variable)

3. Study Design

3.1 Design

The trial is a multicenter, superiority, open-label, phase III randomized controlled trial. Patients fulfil the eligibility criteria as outlined in the protocol are invited to participate the trial consecutively and randomized individually to the control or experimental group. Randomization is based on the random block design (block size of 4).

3.3 Interventions

3.3.1 Experimental arm: IVIG + Aspirin + Prednisolone

Patients in this arm will receive conventional IVIG treatment plus additional prednisolone 2 mg/kg per day in the initial treatment. The details are as follows:

In both arms, IVIG treatment is administered within 12 to 24 hours with the maximum dose of 60g. The dose of aspirin will be reduced to 3 to 5 mg/kg per day when fever subsides for 3 days and CRP is normal, and continued for at least 6 weeks after onset of KD. If patients resistant to initial IVIG therapy will be given rescue therapy, including a second dose of IVIG (2 g/kg), or a high dose of methylprednisolone (10 to 30 mg/kg per day), or infliximab (5 mg/kg), or other immunosuppressive agents, or a combination with two or more drugs, or even more aggressive treatment such as plasmapheresis, depending on patients' condition and physicians' experience. IVIG resistance is defined as recurrent or persistent fever (axillary temperature $\geq 37.5^{\circ}\text{C}$ or rectal temperature $\geq 38^{\circ}\text{C}$) after 36 hours of completion of initial IVIG infusion.

Patients in the experimental group will additionally receive intravenous methylprednisolone 1.6 mg/kg per day which is given in 2 doses (equal to prednisolone 2 mg/kg, and the maximum dose is 60 mg of prednisolone), then switch to oral prednisolone 2 mg/kg when fever subsides for 3 days. If CRP returns to normal, the prednisolone dose will be tapered over 15 days in 5-day steps, from 2 mg/kg per day to 1 mg/kg per day then to 0.5 mg/kg per day. During corticosteroids administration, 0.5 mg/kg H2-blocker omeprazole will be given per day.

3.3.2 Control arm: Standard Treatment: IVIG + Aspirin

Patients in this arm will receive conventional treatment including, IVIG 2 g/kg and oral aspirin 30 mg/kg per day (given at 3 divided doses) in the initial treatment, which has been elaborated in the corresponding section of 3.3.1.

3.4 Randomization and Blinding

Randomization is stratified by trial sites and done in block size of 4. According to the random seeds, a sequence of study numbers and allocation plan will be generated by the SAS software (version 9.4). Each allocation sequence will be placed in four small, opaque and sealed envelopes numbered in order from 1 to 4, and then enclosed in a larger, opaque and sealed envelope marked with the block number. The randomized plan and concealed envelopes will be prepared by an independent statistician team from the Clinical Trial Unit (CTU) of the Children's Hospital of Fudan University, and delivered to and kept by the site coordinate nurse. Recruited patients will be randomly allocated in a 1:1 ratio to the control or experimental group based on the randomization plan. At each site, after obtaining signed informed consent from the eligible participant, the trained physician will meet with the prespecified institutional nurse to achieve the allocation plan as indicated by the corresponding envelope. The coordinate nurse will open the envelopes in numbered order according to the enrollment order, reveal the treatment allocation to the physician, and record the assignments of the enrolled patient.

Patients and physicians who treat patients will not be masked to the allocation, while pediatric cardiologists who assess CAL by echocardiography will be blinded to the allocation. All researchers conducting outcome assessments will be masked in the trial. The trial statistician will also be blinded regarding the treatment code when developing the statistical analysis plan and writing the statistical programs, which will be validated and completed using dummy randomization codes. The actual allocation will only be provided to the study team after lock of the database.

3.5 Sample Size

This study is a superiority trial. Sample size calculation is performed based on the difference of the primary outcome between the two arms. According to the previous study³, we assume a difference in the proportion of patients with CAL occurred within the first month of illness between the two groups of 3.3% (12.4% vs 9.1%, odds ratio [OR] = 0.73 for the control arm and the experimental arm, respectively). With an α of 0.05 and a power of 0.8, a sample size of 1400 cases in each group will be needed. With an assumed dropout rate of 10%, a total of 3200 patients are planned for recruitment (1600 per arm).

4. Analysis Populations

4.1 Study Population Data Sets

Three study populations will be considered in the analysis. The primary analysis for the primary objective will be based on the intention-to-treatment population.

Intention-to-Treat population

Intention-to-treat (ITT) population will be defined at the moment the randomization is performed, including all subjects who are randomized.

Participants will be excluded from the ITT analysis if the primary outcome is missing, forming a modified ITT population (mITT).

Per-protocol population

Participants will be excluded from the per-protocol (PP) population if they:

- Being randomized but not receiving any treatment.

- Not adhering to allocated treatment due to:
 - aspirin allergy in either group.
 - being allocated to the experimental arm, while not completing the prednisolone treatment as recommended by the protocol (i.e., stopped early, took less than the recommended doses or tapered more quickly than the recommended period).
 - being allocated to the control arm but were prescribed additional prednisolone treatment due to discovered with IVIG resistance or other co-morbidities, such as juvenile idiopathic arthritis and necrotic lymphadenitis.

The treatment groups in the PP analysis will be determined according to what the participant actually received. This population will be used for the supportive analyses.

Safety population

Participants given any medicine-relate-treatments will be included in this population. Adverse reactions and events will be recorded. This population will be used for the safety analyses.

4.2 Study Close Date

The data collection close date is the date on which the last patient completed 6-month follow-up.

All the participants will be followed up for 12 months.

4.3 Data Monitoring and Cleaning

Each center has a data manager dedicated to managing the data. Feedback on the inclusion of the week's study subjects is provided weekly in a WeChat group. All databases are synchronized in the cloud using NutCloud. The center data administrator verifies each sub-center database on a monthly basis. The data will then be checked to ensure that there are no erroneous entries and that all missing data is properly coded.

4.4 Data Check-up

Once all data have been inputted and checked, the database will be locked and a data download request made. The data will be downloaded into SAS, R and Stata formats for statistical analyses.

5. Statistical Analyses

5.1. Primary Outcome Analysis

5.1.1 ITT analysis of the primary outcome - the primary analysis

The primary analysis will be based on the ITT population as defined above. The primary outcome is a binary outcome: CAL occurs or not within 1 month of illness onset. Since CAL will be repeatedly examined at enrollment, 2 weeks, 1 month, 3 months, 6 months and 12 months respectively, generalized estimating equation (GEE) model will be performed, with treatment, visit and interaction between treatment with visit as fixed effect, patient ID as cluster effect, the mean of 5 coronary artery baseline z scores (described in section 2.2.1) as covariate variable. Risk difference (RD) and two-sided 95% confidence intervals (CI) between the two treatment groups will be estimated from the model using a binomial distribution and identity link function. OR with 95% CI at each time point will be obtained using GEE model with binomial distribution and logit link function. Binomial distribution and log link function will be used to obtain estimation of risk ratio (RR) and 95% CI. Exchangeable correlation structure is assumed for within-group variation for all the GEE models. The P value for the interaction term will be used to determine the statistical significance of the group difference at specific time point.

If the above GEE model does not converge, a poisson distribution will be used for the family function. A negative binomial distribution will be subsequently used for family function in case the GEE model based on poisson distribution does not converge. RD, OR and RR with their 95% CI

estimates will be reported by using identity, logit and log link function, respectively. In the final analysis, a normal family distribution was used because none of the three prespecified distribution models converged. RD and 95% CI estimates were derived using identity link function.

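### Section 5.1.1 decides the 1-month group difference on the treatment-by-visit interaction P value, which does not test that difference

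*SAP*

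**What the plan says.** Section 5.1.1 specifies a GEE "with treatment, visit and interaction between treatment with visit as fixed effect", with patient as cluster and the mean of the five baseline z scores as covariate. Its significance rule is one sentence: "The P value for the interaction term will be used to determine the statistical significance of the group difference at specific time point". Neither the visit coding nor the reference visit is given.

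The hypothesis concerns a single visit. Section 2.1 says "IVIG treatment plus prednisolone will reduce the incidence of CAL at 1 month of illness comparing with the conventional IVIG treatment". Section 2.2.1 says "The primary outcome is the occurrence of coronary artery lesions (CAL) at one month from disease onset". Section 3.5 sizes the trial on a simple difference in proportions: "we assume a difference in the proportion of patients with CAL occurred within the first month of illness".

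The visits that enter as responses are not listed. Section 5.1.1 justifies the GEE with "Since CAL will be repeatedly examined at enrollment, 2 weeks, 1 month, 3 months, 6 months and 12 months respectively", which includes enrollment, while Section 2.2.1 describes that examination as "at admission before treatment as the baseline". Table 2 starts at 1 month.

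For the analysis as run, Section 5.1.1 reports a normal-family model and says "RD and 95% CI estimates were derived using identity link function". It does not say which P value was reported.

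**The concern.** The interaction P value answers a different question from the one the trial was designed to answer, and it can disagree with the 1-month RD and 95% CI from the same model. A benefit of similar size at every follow-up visit could be declared non-significant. An effect confined to another visit could make 1 month appear significant. How large the problem is depends on a reference visit and a set of response visits that the SAP leaves open.

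The rule also carries over by reference to the per-protocol analysis (5.1.2.1), the subgroups (5.1.3) and repeated binary outcomes (5.2.1).

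**Working it through.** **Algebra.** With reference coding, the group difference at visit v is b_trt + b_int(v), and b_trt is the difference at the reference visit. Hence b_int(1 month) = RD(1 month) − RD(reference).

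- Reference = enrollment: randomisation makes the expected RD there zero. The coefficient has the right expected value on the identity scale and the test keeps its size, but its variance differs.
- Reference = a post-baseline visit: any effect at that visit is subtracted from the 1-month effect.
- Reference = 1 month: there is no 1-month interaction coefficient to test.
- Joint test of all interaction terms: the null hypothesis is a constant effect over visits, not a zero effect at 1 month.

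The sentence would be correct only if treatment were nested within visit with no main effect. The SAP includes the main effect.

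**Inputs.** From Section 3.5: 12.4% vs 9.1%, two-sided 5%, 80% power, 1400 per arm. CAL rates at other visits and all within-patient correlations (rho) are my assumptions. The baseline z-score covariate is left out.

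**Reproducing the SAP's figure.** The variances are 0.124 × 0.876 = 0.108624 and 0.091 × 0.909 = 0.082719, sum 0.191343. Then n = (1.960 + 0.842)² × 0.191343 / 0.033² ≈ 1380 per arm, in line with 1400. The sample size therefore rests on a direct comparison of two proportions.

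**1-month contrast.** SE = √(0.191343/1400) = 0.01169 and 0.033/0.01169 = 2.82, giving 80.6% power.

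**Single interaction coefficient.** The variance per arm is [p1q1 + p0q0 − 2·rho·√(p1q1·p0q0)]/1400, where p1 is the 1-month rate, p0 the reference-visit rate, and q = 1 − p. Example with enrollment CAL 20% and rho 0.2: the numerators are 0.2159 (control) and 0.1967 (experimental), so SE = √(0.4126/1400) = 0.01717. Then 0.033/0.01717 = 1.92, giving 49% power.

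| Reference visit | Assumed rates | rho | Power |
|---|---|---|---|
| Enrollment | 10% both arms | 0.2-0.5 | 62-82% |
| Enrollment | 20% both arms | 0.2-0.5 | 49-67% |
| Enrollment | 30% both arms | 0.2-0.33 | 42-47% |
| Enrollment | 12.4% both arms | 0.7 | 94% |
| 12 months | 4% vs 3.0-4.0% | 0.2-0.5 | 46-90% |
| 2 weeks | 18% vs 14.7% (also 3.3 points) | any | 5% |

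The 2-week row takes enrollment as not a response visit. If in that case there is no 1-month effect (12.4% in both arms), the 1-month coefficient is significant 50-70% of the time at rho 0.2-0.5.

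**Can high correlation rescue the enrollment case?** Two binary outcomes with rates a < b cannot correlate above √(a(1−b)/(b(1−a))). Here that ceiling (control/experimental) is 0.75/0.63 at 20% enrollment CAL, 0.65/0.55 at 25% and 0.57/0.48 at 30%. With each arm at its ceiling, power is 85%, 71% and 60%. Above about 21.5% enrollment CAL, no attainable correlation recovers 80.6%.

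**Joint test** (Wald chi-square on all interaction terms, exchangeable rho 0.2-0.33, noncentral chi-square):

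- Fading effect, six visits (5 df), control 10 or 20/18/12.4/7/5/4%, experimental 10 or 20/14.7/9.1/5.5/4.3/3.5%: power 63-74%.
- Constant 3.3-point effect, five post-baseline visits (4 df), control 18/12.4/8/7/6%: power 5%.
- 3.3-point effect at 2 weeks only and none at 1 month, six visits, control 20/18/12.4/7/5/4%: significant 45-52% of the time.

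A simulation (3000 trials per scenario, 1400 per arm) agrees. The joint test rejected in 61-72%, 4-6% and 44-53% of trials in these three scenarios, against 80-81%, 79-82% and 4-5% for the 1-month contrast.

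**The case against.** The sentence names the group difference at a time point as its target. Section 5.1.1 promises an OR at each time point, Section 6 promises group differences at the prespecified time point, and Table 2 sets out RD, OR and RR by visit with no P-value column. The authors may simply have meant that the interaction model yields visit-specific contrasts. If so, the analysis may be sound and only the wording is wrong.

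Much of this stands. The charitable reading is plausible, and harm in the analysis as run is not shown. The power figures depend on assumed rates, correlations and reference visit and run from 5% to 94%, so no single loss follows. Omitting the baseline covariate means that 80.6% is not exactly the power of the SAP's own model. Nothing points to a 2-week reference, so that row is a worst case and not a forecast. A visit can be both a baseline and a response, so Sections 2.2.1 and 5.1.1 do not contradict each other there; the response visits are just not stated. The reach through Section 5.2.1 is also narrow, because no listed secondary outcome is a repeated binary variable and Section 5.2.4 sends only the exploratory medium-to-giant aneurysm outcome down that route.

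The objection does not supply another rule. Sections 6 and 6.2 promise estimates and name no test, so the interaction sentence remains the only significance criterion for the primary analysis, and it names the wrong quantity.

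**Conclusion.** The concern holds and must be fixed, because this is the only decision rule for the primary hypothesis and under neither reading does it test the 1-month difference. That conclusion follows from the model terms and needs no assumption.

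The size of the harm is conditional. With enrollment as the reference the test is valid, and the usual cost is power, although high correlation with low baseline CAL can remove or reverse the loss. With a post-baseline reference or a joint test, a steady benefit can be missed almost entirely, and an effect at another visit can be mistaken for one at 1 month. Whether any of this affected the reported result cannot be learned from the SAP.

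**What to change.** Replace the sentence in Section 5.1.1 with: *Primary significance is judged by the two-sided Wald test of the between-group contrast at 1 month (treatment main effect plus treatment-by-1-month interaction), from the same model, scale and standard error as the reported RD and 95% CI. The interaction P value is reported only as a test of whether the effect changes over visits.* State the visit coding, the reference visit and whether enrollment is a response visit. Apply the same rule to the analyses that refer back to Section 5.1.1.

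Because the final analysis has been run, first state which contrast produced the reported P value. If it was the 1-month contrast, only the SAP wording needs correcting. If it was the interaction term, report the 1-month contrast as a disclosed correction with the interaction P value beside it.

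The cost is one sentence and one disclosure and, only in the second case, one contrast statement on the locked data. No new data are needed and the sample size is unaffected.

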5.1.2.2 Covariate adjusted analysis of the primary outcome

An analysis of the primary endpoint will be adjusted for baseline information including age, body mass index (BMI), gender and complete or incomplete KD (following the KD diagnostic criteria from the American Heart Association released in 2017). From the above model, the adjusted estimates of RD and two-sided 95% CIs will be derived. The OR and RR with their 95% CIs will also be estimated from the GEE model using logit and log link function as described in Section 5.1.1.

Given the GEE model in the primary analysis has converged, if the GEE model doesn't converge when all covariates are introduced into the model simultaneously, the adjusted model will be established by removing a covariate one by one until the model converges.

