6.2 Graphical Displays

Table 1. Baseline characteristics of patients

Analysis Set: ITT population

Variable	Statistic	Treatment A (N=)	Treatment B (N=)	All (N=)
Gender, n (%)	Female			
	Male			
Age (years)	n			
	Mean (SD)			
	Median (IQR)			
	Min-Max			
Height (cm)	n			
	Mean (SD)			
	Median (IQR)			
	Min-Max			
Weight (kg)	n			
	Mean (SD)			
	Median (IQR)			
	Min-Max			
LMCA	n			
	Mean (SD)			
	Median (IQR)			
	Min-Max			
LAD	n			
	Mean (SD)			
	Median (IQR)			
	Min-Max			
LCX	n			
	Mean (SD)			
	Median (IQR)			

Variable	Statistic	Treatment A (N=)	Treatment B (N=)	All (N=)
	Min-Max			
RCA (prox)	n			
	Mean (SD)			
	Median (IQR)			
	Min-Max			
RCA (mid)	n			
	Mean (SD)			
	Median (IQR)			
	Min-Max			

Table 2. Summary for primary outcomes by generalized estimating equation model
Analysis Set: ITT population

		Participants, No. (%)		Generalized estimating equation model analysis		
Primary outcome	Visit	Treatment A	Treatment B	Risk difference (95% CI)	Odds Ratio (95% CI)	Risk ratio (95% CI)
Covariate unadjusted ^a						
CAL	1 month					
	3 months					
	6 months					
	12 months					
Covariate adjusted ^b						
CAL	1 month					
	3 months					
	6 months					
	12 months					

^aThe GEE model only includes the mean of 5 coronary artery baseline z scores as covariate.

^bThe GEE model was adjusted by including ...as covariates.

Table 3. Subgroup analysis of primary outcome by generalized estimating equation model

Analysis Set: ITT population

			Participants, No. (%)		Generalized estimating equation model analysis		
Primary outcome	Variable	Visit	Treatment A	Treatment B	Risk difference (95%CI)	Odds ratio (95%CI)	Risk ratio (95%CI)
CAL	Age (<=1 year)	1 month					
		3 months					
		6 months					
		12 months					
	Age (>1 year)	1 month					
		3 months					
		6 months					
		12 months					
	Gender (F)	1 month					
		3 months					
		6 months					
		12 months					
	Gender (M)	1 month					
		3 months					
		6 months					
		12 months					
	BMI (I)	1 month					
		3 months					
		6 months					
		12 months					
	BMI (N)	1 month					
		3 months					
		6 months					
		12 months					
	BMI (H)	1 month					
		3 months					
		6 months					

			Participants, No. (%)		Generalized estimating equation model analysis		
Primary outcome	Variable	Visit	Treatment A	Treatment B	Risk difference (95%CI)	Odds ratio (95%CI)	Risk ratio (95%CI)
		12 months					

Table 4. Secondary analysis by generalized estimating equation model
Analysis Set: ITT population

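### The non-convergence rule for the primary model had no workable route to the risk difference, and the normal-family model that replaced it is not fully specified

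*SAP*

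**What the plan says.** Section 5.1.1 of the SAP fits a GEE with treatment, visit and their interaction, an exchangeable working correlation, and "the mean of 5 coronary artery baseline z scores (described in section 2.2.1) as covariate variable". The RD with its confidence interval "will be estimated from the model using a binomial distribution and identity link function". The OR comes from the logit link and the RR from the log link.

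The non-convergence rule has two steps: "If the above GEE model does not converge, a poisson distribution will be used for the family function", and then "A negative binomial distribution will be subsequently used for family function in case the GEE model based on poisson distribution does not converge". The same three links are kept for RD, OR and RR under the new families.

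The section closes with a report in the past tense: "In the final analysis, a normal family distribution was used because none of the three prespecified distribution models converged". It adds that the RD and its interval came from the identity link, and says nothing of OR or RR for that model. The shell "Table 2. Summary for primary outcomes by generalized estimating equation model" in Section 6.2 has columns for all three measures at 1, 3, 6 and 12 months.

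The exchangeable structure is the only covariance statement. No section names a robust, sandwich or empirical variance. Section 6 names SAS as the main software and allows Stata or R for some analyses.

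**The concern.** A fallback rule should remove the likely reason for failure. This one changes the variance function and leaves the mean model as it was. Binomial, Poisson and negative binomial variances are all defined only for positive means. With an identity link, the fitted mean is a straight line in the baseline z score and can fall below zero. If that stops the first fit, it can stop the other two as well.

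Two things are at stake. First, the confirmatory estimate comes from a model that no rule selected. The same method is carried into most of the sensitivity analyses in Section 5.1.2, the subgroups in 5.1.3 and the repeated binary outcomes in 5.2.1. Second, a normal family uses one residual variance for every visit, whereas the variance of a yes/no outcome follows its risk. That does no harm to robust standard errors but matters for model-based ones, and the SAP does not say which were used.

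**Working it through.** **The plan's own figure.** Section 3.5 gives 12.4% against 9.1%, alpha 0.05, power 0.80 and 1,400 per arm. With pooled risk 0.1075:

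n = [1.96 × √(2 × 0.1075 × 0.8925) + 0.8416 × √(0.124 × 0.876 + 0.091 × 0.909)]² / 0.033² = (0.8586 + 0.3681)² / 0.001089 ≈ 1,382 per arm.

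This agrees with 1,400. No stated number is in dispute; these rates anchor the checks below.

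**Why changing the family does not help.** At a given visit the planned model reads: risk = p + b × (z − mean z). It has no z-by-visit term, so one slope b serves all visits. The fitted risk is negative when z lies more than p/b below its mean. Take an assumed 12-month risk of 2% to 6%. A child one unit below the mean then has a negative fitted risk once b exceeds 0.02 to 0.06 per unit. Nothing in this depends on the family.

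**Simulated convergence.** Inputs from the SAP: 1,400 per arm, 12.4% and 9.1% at 1 month, exchangeable correlation, treatment by visit, baseline z covariate. Assumed: risks at the other visits, the z distribution (SD 0.5 and 1.0) and the z effect. Data sets that converged:

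| Family and link | Five post-baseline visits | Two further small runs |
|---|---|---|
| Binomial, identity | 0/10 | 0/6, 0/8 |
| Poisson, identity | 0/10 | 0/6, 0/8 |
| Negative binomial, identity | 0/10 | not run |
| Normal, identity | 10/10 | not tabulated |
| Binomial, logit | 10/10 | 6/6, 8/8 |
| Binomial, log | 0/10 | not run |
| Poisson, log | 10/10 | not run, 8/8 |

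In the normal fits about 6% (z SD 0.5) to 21% (z SD 1.0) of fitted risks were below zero. On this evidence the rule works for the RR, because Poisson-log rescues binomial-log. The OR needs no rescue. Only the RD has no route.

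**Variance by visit.** Under a normal family, a pooled variance replaces p(1 − p):
- enrollment, assumed 20% to 40%: 0.160 to 0.240
- 1 month, 12.4%: 0.124 × 0.876 = 0.109
- 12 months, assumed 2% to 6%: 0.020 to 0.056

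A pooled value is too small where risk is high and too large where it is low. Simulated model-based SE divided by robust SE:
- 1 month: 0.97 to 1.02 with enrollment among the visits. With post-baseline visits only, 0.0101/0.0109 = 0.93 (z SD 1.0) and 0.0104/0.0114 = 0.91 (z SD 0.5). A further run gave 0.92 to 1.07, depending on whether enrollment counts as a visit.
- 3 months: 1.10 to 1.41.
- 12 months: 1.31 to 1.85.

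At a 1-month ratio of 0.91 to 0.93, the effective critical value is about 1.79 to 1.82 instead of 1.96, so a nominal 5% test runs at about 7%.

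**The alternative.** A logistic model at 1 month, standardized over baseline z, converged in 30 of 30 simulated trials. One model gave RD −3.1 points, RR 0.76 and marginal OR 0.73. The design RD is −3.3 points, and the Monte Carlo error is about 0.0108/√30 = 0.2 points. In a separate run the SE of the RD was 0.0108 by logistic standardization and 0.0110 (robust) from the normal GEE, about 2% smaller.

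**The case against.** The strongest reply is that the primary result may hardly change. The primary time point is 1 month. There the model-based and robust standard errors are close in some scenarios, and standardization alters the SE by about 2%. With robust standard errors, a normal family with identity link is a usable estimator of a randomized RD, and negative fitted risks do not by themselves bias it. The sponsor also disclosed the switch. Section 5.1.2.10 gives an unadjusted binomial-identity GLM that avoids the covariate problem, although it was added at manuscript revision. All of this stands, and it limits the size of the point.

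Five stronger readings are tempting, and the document supports none of them:
- **The identity link is the proven cause.** The SAP gives neither the cause nor the failing link. The simulations show a mechanism, with few data sets, a cap of 30 or 40 iterations in the fits for which it is recorded, and assumed z inputs.
- **OR and RR were abandoned.** The text is silent on their source; it does not say they were dropped.
- **The reported intervals are wrong.** That holds only if model-based standard errors were used, which no section states.
- **Poisson is illegitimate for a yes/no outcome.** In a GEE the family is a working variance, and Poisson is acceptable with robust standard errors.
- **The adjusted analysis is left undefined.** Section 5.1.2.2 applies once the primary model has converged, and the normal model can be read as meeting that. The fair remark there is narrower: "removing a covariate one by one until the model converges" states no order of removal, and it concerns a sensitivity analysis.

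**Conclusion.** The point holds in a limited form. The rule for the confirmatory analysis left the RD without a workable fallback, all three planned families failed, and an unplanned model supplied the estimate. The text establishes the failure and the switch. The reason is a well-supported inference.

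The replacement model is incompletely specified: its variance estimator and the source of OR and RR are not stated. If model-based standard errors were used, the 1-month SE would be roughly 0.9 to 1.07 times the robust one, and the 3- to 12-month intervals would be too wide by a factor of about 1.1 to 1.85. If robust ones were used, that error does not arise. These sizes rest on assumed risks at the other visits, an assumed z distribution and effect, and the choice whether enrollment enters as a visit. A reader might infer that the primary conclusion is unsafe; nothing in the document shows that. This should be corrected, but it does not overturn the trial's analysis.

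**What to change.** 1. Keep the original rule on record. Label the normal-family, identity-link RD as a post hoc departure and report it with empirical sandwich standard errors, stating this in Section 5.1.1.
2. Add the 1-month RD and RR, with intervals, by marginal standardization of the binomial-logit GEE already planned for the OR (sandwich delta method or patient-level bootstrap). Label it as added after the planned models failed. For any analysis not yet run, such as 12 months, make this the fallback in place of further family changes.
3. Report the OR from the logit GEE, and show the unadjusted binomial-identity GLM of Section 5.1.2.10 beside it.

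Deleting the planned steps, or promoting standardization to sole primary model now, would be a second choice made after the results and would blur the record. The cost is some SAP wording and a small amount of extra analysis on existing data. The downside is one more estimate that must carry a post hoc label.
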